[Part 2 of 2 of the document. The other parts are not shown.]

All AEs are coded; details are described in the trial-specific Data Management Plan.

If an event classifies as a AESI, the investigator must tick the AESI box on the AE form and complete the AESI form. The AESI form will capture if the event was associated with any signs or symptoms and capture the highest/lowest blood pressure and pulse measured during the event. The investigator must report all AESIs to the sponsor's responsible pharmacovigilance unit (Safety CRO; see the list of trial personnel in Section 12.1) immediately (within 24 hours) after obtaining knowledge about the event.

The investigator must report initial information electronically (e.g. in PDF format) on all SAEs to the sponsor's responsible pharmacovigilance unit (Safety CRO; see the list of trial personnel in Section 12.1) immediately (within 24 hours) after obtaining knowledge about the event. The Safety CRO will inform the medical monitor and the sponsor about the reported SAEs.

It is the responsibility of the Safety CRO to report all SUSARs (see Section 7.2.1.1) that occur in this trial to the Competent Authorities and Institutional Review Boards (IRBs)/Independent Ethics Committees (IECs) in accordance with the local requirements in force and ICH guideline for GCP. The trial monitor must be informed accordingly.

7.2.1.3 Follow-up of adverse events

All AEs that are ongoing at the end of the subject's participation in the trial will be followed-up until the event is resolved or reaches a satisfactory outcome as deemed by the investigator or until the last visit of the last subject enrolled in the trial, whichever occurs first.

Follow-up actions for all SAEs will be performed according to appropriate clinical care practices and may depend on the nature of the event. These will be determined after internal review and/or sponsor review.

The follow-up information should only include new (updated and/or additional) information that reflects the situation at the time of the investigator's signature.

Follow-up information on (S)AEs will be updated using the (S)AE form. If a non-serious event becomes serious during the follow-up the AE form and SAE form have to be used and reporting timelines follow those of an SAE.

The investigator must forward follow-up information on SAEs and if previously non-serious AEs become SAEs to the Safety CRO immediately (within 24 hours) after obtaining knowledge about the new information.

The sponsor and/or CROs acting on behalf of the sponsor can upgrade a non-serious AE to an SAE. In these situations the investigator will be informed and asked to fill out an SAE form and forward to the Safety CRO immediately (within 24 hours).

7.2.1.4 Clinical laboratory abnormalities and other abnormal assessments as adverse events or serious adverse events

Abnormal laboratory findings (e.g. biochemistry, hematology, urinalysis) or other abnormal assessments (e.g. vital signs) that are judged by the investigator as **clinically significant** will be recorded as AEs or SAEs if they meet the definition of an AE or SAE. Clinically significant abnormal laboratory findings or other abnormal assessments that are detected during the trial or are present at baseline and significantly worsen following the start of the trial will be reported as AEs or SAEs. However, clinically significant abnormal laboratory findings or other abnormal assessments that are associated with the disease being studied, unless judged by the investigator as more severe than expected for the subject's condition, or that are present or detected at the start of the trial and do not worsen, will not be reported as AEs or SAEs.

The investigator will exercise his or her medical and scientific judgment in deciding whether an abnormal laboratory finding or other abnormal assessment is clinically significant.

7.2.2 Hypoglycemia

Hypoglycemia will be regarded as an AE and recorded and documented on an AE form (and SAE form, if applicable).

Hypoglycemia is defined as a decline in plasma glucose to below 70 mg/dL (3.9 mmol/L). However, in the time period from initiation of the hypoglycemic clamp procedure (see Section 8.2.3.1) until 45 minutes after dosing, hypoglycemia is defined as a decline in plasma glucose to below 45 mg/dL (2.5 mmol/L).

During the dosing visit, prior to administration of the IMP, a plasma glucose value of <45 mg/dL (2.5 mmol/L) will be treated by an IV glucose solution. After administration of the IMP in the period from 8 minutes until 44 minutes after dosing, a plasma glucose value of <45 mg/dL (2.5 mmol/L) will be treated by an IV glucose solution, and if a plasma glucose value of \geq 70 mg/dL (3.9 mmol/L) is not achieved within the 45 minutes after IMP administration, IV glucose infusion will also be initiated.

If the subject experiences symptoms of hypoglycemia, a plasma glucose measurement should be taken in order to classify the event (please refer to Section 7.4.2 for additional details).

7.2.3 Physical examination

The physical examination will be carried out at screening (Visit 1) and at the follow-up visit (Visit 3; see Table 3).

The physical examination includes examination of the following body systems: head, ears, eyes, nose, throat, including the thyroid gland; heart, lung, chest; abdomen; skin and mucosae; musculoskeletal system; nervous system; lymph node; other findings.

At the screening visit, any abnormality will be recorded and described in the eCRF, including the investigator's assessment of clinical significance ('abnormal, not clinically significant' or 'abnormal, clinically significant'). Clinically significant findings at the screening visit should be recorded as concomitant illness.

At subsequent visits, any clinically significant deterioration of a pre-existing condition as well as any new clinically significant findings will be recorded as AEs (see Section 7.2.1).

7.2.4 Vital signs

An examination of the following vital signs will be performed at screening (Visit 1), the dosing visit (Visit 2) and at the follow-up visit (Visit 3):

- Diastolic and systolic blood pressure (mmHg) will be measured after at least 5 minutes rest in a supine position. At Visit 1, blood pressure will be measured in both arms. The blood pressure from the arm with the higher systolic value is

transcribed into the eCRF and this arm should be used for all subsequent measurements of the subject's blood pressure in this trial.

- Pulse (beats per min) measured after at least 5 minutes rest in a supine position.
- Body temperature (°C).

At the dosing visit, measurements will be taken prior to the start of the insulin-induced hypoglycemic procedure (within 30 minutes) and at 30, 90, and 300 minutes after dosing (see [Table 3](#)). The actual time of the assessment should not deviate from the nominal time by more than ± 10 minutes. In addition to the pre-specified assessments as listed in [Table 3](#), blood pressure and pulse may be assessed at any time during the trial at the discretion of the investigator.

7.2.5 *Electrocardiogram*

A standard 12-lead ECG will be performed at the screening visit (Visit 1), the dosing visit (Visit 2; prior to the start of the insulin-induced hypoglycemic procedure [within 30 minutes]) and at 20, 35, 45, 60, and 300 minutes after dosing) and at the follow-up visit (Visit 3; see [Table 3](#)). The actual time of the assessment should not deviate from the nominal time by more than ± 5 minutes.

ECG parameters (heart rate, PQ, QRS, QT, QTcB) and any abnormality will be recorded and described in the eCRF including the investigator's assessment of clinical significance ('abnormal, not clinically significant' or 'abnormal, clinically significant').

At subsequent visits, any clinically significant deterioration of a pre-existing condition as well as any new clinically significant findings will be recorded as AEs (see Section [7.2.1](#)).

7.2.6 *Local tolerability*

Immediately prior to treatment administration, it should be verified that the injection site is normal. To ensure all injection site assessments are performed at the injection site, the site will be marked with a pen prior to injection. Assessment of local tolerability at the injection site will be performed at the dosing visit (Visit 2; at 30, 120 and 300 minutes after dosing), and at the follow-up visit (Visit 3) (see [Table 3](#)) and more frequently, if deemed necessary by the investigator. The actual time of the assessment should not deviate from the nominal time by more than ± 10 minutes. In the eCRF, the time of assessment and any injection site reaction observed will be recorded. In case of an observation, the Local Tolerability form will be completed, as well as the (S)AE form.

The local tolerability at the injection site will be evaluated by means of the following assessments: spontaneous pain, pain on palpation, itching, redness, edema,

induration/infiltration, and other. Each of these assessments will be reported on a scale of 0 (none), 1 (mild), 2 (moderate), and 3 (severe). The evaluation and the actual time of the assessment will be recorded. The assessments will be performed by a trial physician or nurse.

Digital pictures will be taken of the injection site at the time of identification, and thereafter as often as judged necessary by the investigator. The pictures should include a subject identifier, visit number, time after dosing, and a ruler for scaling.

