9.7.4 Other safety data

Incidence of rescue infusion of IV glucose during the hypoglycemic clamp procedure will be analyzed using descriptive statistics (frequency and percentage) by treatment group. Inferential treatment group comparisons will be assessed via pairwise tests of

independent binomial proportions (dasiglucagon versus placebo, GlucaGen versus placebo).

Time to first rescue infusion of IV glucose during the hypoglycemic clamp procedure will be evaluated using a KM time to event statistical model, with treatment group and injection site as stratification factors. Differences between the KM curves (dasiglucagon versus placebo, GlucaGen versus placebo) will be evaluated inferentially using pairwise two-sided stratified log-rank tests. If the endpoint is never met, the time of the last plasma glucose measurement will be the censoring time.

Vital signs, physical examination, 12-lead ECG and local tolerability data will be summarized using descriptive statistics.

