Besides intravenous (IV) glucose administration, an injectable form of glucagon is given as first aid in cases of severe hypoglycemia, when the patient is unconscious or for other reasons cannot take glucose orally. The approved glucagon dose for an adult is 1 mg, given by intramuscular (IM), IV, or subcutaneous (SC) injection, which quickly raises blood glucose levels. As current marketed recombinant glucagon is highly unstable when dissolved in solution, the injectable form has to be reconstituted prior to use in a 9-step procedure that requires a sterile diluent to be injected into a vial containing lyophilized powdered glucagon. When dissolved in a fluid state, glucagon can form amyloid fibrils (11), or tightly woven chains of proteins made up of the individual glucagon peptides. The reconstitution process makes the use of marketed glucagon products cumbersome (12), and a more patient-friendly formulation is needed. Currently, the Food and Drug Administration (FDA) approved instructions for commercially available glucagon allow only for immediate usage of glucagon after the powder is reconstituted in aqueous solution (13). Therefore, a glucagon analog with enhanced biophysical stability may represent a leap forward in terms of convenient therapeutic applications.

2.1.3 *Dasiglucagon*

Dasiglucagon (ZP4207) is a stable peptide analog of human glucagon, available in a ready-to-use liquid formulation. Dasiglucagon (hereinafter referred to as dasiglucagon) is in development for the treatment of severe hypoglycemia in insulin-dependent patients with diabetes mellitus. Dasiglucagon is a specific and full glucagon receptor agonist designed to mimic the effects of glucagon, having a fast absorption and elimination (minutes). It is a peptide of 29 amino acids, with 7 amino acid substitutions compared to native glucagon. The main purpose of the substitutions is to increase the physical and chemical stability of the glucagon analog compared to marketed glucagon products such as Lilly Glucagon or GlucaGen® (hereafter referred to as GlucaGen). Dasiglucagon exhibits improved physical and chemical stability and is available in an aqueous solution at neutral pH (14).

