2.1.3.1 Pharmacokinetics and pharmacodynamics of dasiglucagon

The results of the phase 1 and 2 clinical trials confirmed dose-proportionality for dasiglucagon PK, which is characterized by a fast absorption with a peak plasma concentration obtained after 35 minutes. Thereafter, the plasma concentration rapidly declines with an average half-life of 28 minutes. The median time to the maximum plasma concentration (t_{max}) was 35 minutes for dasiglucagon compared with 20 minutes for GlucaGen.

At all dose levels in the phase 2 trial, all subjects achieved a plasma glucose level of at least 70 mg/dL (3.9 mmol/L) as well as an increase in plasma glucose by at least 20 mg/dL (1.1 mmol/L) within 30 minutes after dosing. The PD responses to 0.6 mg of dasiglucagon and 1 mg of GlucaGen were comparable.

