2.1.3.2 Safety of dasiglucagon

The safety data for dasiglucagon do not give rise to any safety concerns. No new signals were observed, beyond those related to the pharmacological effect of glucagon agonism. All adverse events (AEs) recorded in the trials were of mild or moderate severity. The most frequently reported systemic AE was nausea, which is a known side effect following administration of glucagon. Headache was the next most frequently reported event, occurring in all dose groups in the phase 2 trial. Injection site reactions were observed only sporadically after administration with either dasiglucagon or GlucaGen and all were mild and transient. The most frequent injection site reaction was erythema, occurring in all treatment groups, including the placebo group, irrespective of dose. Glucagon has been described to exert positive inotropic and chronotropic effects and may therefore cause tachycardia and hypertension. In the phase 1 clinical trials, but not the phase 2 trial, temporary but clinically significant decreases in blood pressure were observed in a few healthy volunteers receiving investigational medicinal product (IMP) doses of at least 1 mg (4 with dasiglucagon and 1 with GlucaGen). This is not considered a safety concern; however, hemodynamic changes after dosing will be considered an adverse event of special interest (AESI).

The phase 1 and 2 results and the safety profile described to date do not give rise to specific safety concerns. For further information, please refer to the Investigator's Brochure (14).

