7.2.4 Vital signs

An examination of the following vital signs will be performed at screening (Visit 1), the dosing visit (Visit 2) and at the follow-up visit (Visit 3):

- Diastolic and systolic blood pressure (mmHg) will be measured after at least 5 minutes rest in a supine position. At Visit 1, blood pressure will be measured in both arms. The blood pressure from the arm with the higher systolic value is

transcribed into the eCRF and this arm should be used for all subsequent measurements of the subject's blood pressure in this trial.

- Pulse (beats per min) measured after at least 5 minutes rest in a supine position.
- Body temperature (°C).

At the dosing visit, measurements will be taken prior to the start of the insulin-induced hypoglycemic procedure (within 30 minutes) and at 30, 90, and 300 minutes after dosing (see [Table 3](#)). The actual time of the assessment should not deviate from the nominal time by more than ± 10 minutes. In addition to the pre-specified assessments as listed in [Table 3](#), blood pressure and pulse may be assessed at any time during the trial at the discretion of the investigator.

7.2.5 *Electrocardiogram*

A standard 12-lead ECG will be performed at the screening visit (Visit 1), the dosing visit (Visit 2; prior to the start of the insulin-induced hypoglycemic procedure [within 30 minutes]) and at 20, 35, 45, 60, and 300 minutes after dosing) and at the follow-up visit (Visit 3; see [Table 3](#)). The actual time of the assessment should not deviate from the nominal time by more than ± 5 minutes.

ECG parameters (heart rate, PQ, QRS, QT, QTcB) and any abnormality will be recorded and described in the eCRF including the investigator's assessment of clinical significance ('abnormal, not clinically significant' or 'abnormal, clinically significant').

At subsequent visits, any clinically significant deterioration of a pre-existing condition as well as any new clinically significant findings will be recorded as AEs (see [Section 7.2.1](#)).

7.2.6 *Local tolerability*

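### Bazett's QTcB is the only rate-corrected QT listed, although the protocol says the drug class may raise heart rate; any between-arm difference in heart-rate change could then appear as a QTc difference

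*Protocol*

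**What the plan says.** Section 7.2.5 of the protocol fixes the ECG variables: "ECG parameters (heart rate, PQ, QRS, QT, QTcB) and any abnormality will be recorded and described in the eCRF". The same list stands in all three protocol versions in the file, and no other rate correction appears in the text shown. Post-dose ECGs are taken "at 20, 35, 45, 60, and 300 minutes after dosing) and at the follow-up visit".

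The investigator rates each abnormality for clinical significance. After screening, "any new clinically significant findings will be recorded as AEs".

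On heart rate, section 2.1.3.2 says: "Glucagon has been described to exert positive inotropic and chronotropic effects and may therefore cause tachycardia and hypertension". Section 2.1.3 adds: "Dasiglucagon is a specific and full glucagon receptor agonist designed to mimic the effects of glucagon". Section 2.1.3.1 reports that median t_max "was 35 minutes for dasiglucagon compared with 20 minutes for GlucaGen".

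The only ECG analysis statement is in section 9.7.4: "Vital signs, physical examination, 12-lead ECG and local tolerability data will be summarized using descriptive statistics". QT is of stated interest all the same. Drugs known to prolong it are an exclusion criterion (section 5.4) and are prohibited during the trial (section 6.9.1).

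**The concern.** Bazett's formula divides QT by the square root of RR. If QT in fact changes less steeply with RR than that, the formula takes out too much when the heart speeds up, and the corrected value rises with no change in repolarisation. The protocol itself gives a reason why heart rate may differ between the active arms and placebo, and it places ECGs at the median t_max of both active drugs.

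Two things are exposed. One is the set of by-arm descriptive QTc summaries. With no test or threshold planned, readers will take these at face value, so a rate difference could look like a QT signal or offset a real one. The other is the investigator's significance rating, made when QTcB is the only corrected interval on the list, and any adverse event recorded from it.

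**Working it through.** The plan gives no QTc figure to reproduce, so the check is how far QTcB moves when repolarisation is held constant and only heart rate changes.

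**Inputs from the protocol.** Recorded variables: heart rate, QT and QTcB (7.2.5). ECG times: 20, 35, 45, 60 and 300 minutes (7.2.5). Median t_max: 20 minutes for GlucaGen and 35 for dasiglucagon (2.1.3.1). Size of any heart-rate effect: not given.

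**Assumptions, not in the protocol.** Resting rate 65 bpm (range 60 to 70). Heart-rate rise of 5 to 20 bpm. Corrected QT of c = 400 ms (range 380 to 420). QT-RR exponent e between 0.25 and 0.50.

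**Formulas.** RR = 60/HR. QT = c × RR^e. QTcB = QT/RR^0.5 = c × RR^(e − 0.5). QTcF = QT/RR^(1/3) = c × RR^(e − 1/3). QTcB rises with heart rate if e is below 0.5, is flat at 0.5, and falls above it.

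**One case in full, e = 1/3.**
- At 65 bpm: RR = 0.923 s, QT = 389 ms, QTcB = 400 × 0.923^(−1/6) = 405.4 ms.
- At 75 bpm: RR = 0.800 s, QT = 371 ms, QTcB = 400 × 0.800^(−1/6) = 415.2 ms.
- Change in QTcB: +9.8 ms. Change in QTcF: 0.

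**Other heart-rate rises, e = 1/3, from 65 bpm.** To 70 bpm: +5.0 ms. To 80: +14.3 ms. To 85: +18.5 ms. Over resting rates of 60 to 70 bpm and c of 380 to 420 ms, a 10 bpm rise gives 8.8 to 10.9 ms and a 20 bpm rise gives 16.7 to 20.6 ms.

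**Other exponents, 65 to 75 bpm, c = 400 ms.** Each entry is 400 × (0.800^k − 0.923^k), with k = e − 0.5 for QTcB and k = e − 1/3 for QTcF.

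| e | Change in QTcB (ms) | Change in QTcF (ms) |
|---|---|---|
| 0.25 | +14.9 | +4.8 |
| 1/3 | +9.8 | 0.0 |
| 0.40 | +5.8 | −3.8 |
| 0.45 | +2.9 | −6.6 |
| 0.50 | 0.0 | −9.3 |

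QTcF is not exact either. Its error is the smaller one when e lies below about the midpoint of the two exponents, (1/3 + 1/2)/2 = 0.417.

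**From within-subject change to between-arm difference.** All the figures above are changes within a subject. They become a between-arm difference only to the extent that heart-rate change differs by arm. At e = 1/3:
- active 65 to 75 and placebo unchanged: +9.8 ms
- active 65 to 75 and placebo 65 to 70: 9.8 − 5.0, about +5 ms
- both arms 65 to 75: 0
- placebo 65 to 75 and active 65 to 70: about −5 ms

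**Recoverability.** At 80 bpm (RR 0.75 s) a recorded QT of 363 ms gives QTcB = 363/0.75^0.5, about 420 ms, and QTcF = 363/0.75^(1/3), about 400 ms. Both inputs are already on the list in 7.2.5.

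**The case against.** The strongest reply is that 7.2.5 is a data-collection list. It does not say that QTcB will be the interval tabulated. Section 9 leaves detailed methods to a SAP that is not shown and may already derive QTcF. Heart rate and uncorrected QT are both recorded, so nothing is lost. This stands as far as cost and severity go. It does not remove the point: the protocol names a correction rather than staying silent, and that is the corrected value listed when the investigator rates the ECG. A QTcF derived only at analysis would not revise those ratings.

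A reader might infer several stronger things that the documents do not support:
- **That the protocol expects tachycardia.** It says the class may cause it and gives no size. The hemodynamic finding it reports from phase 1 is a fall in blood pressure (2.1.3.2), and the events of special interest include bradycardia (7.2.1.1).
- **That the active arms will show spurious prolongation against placebo.** Every arm has insulin-induced hypoglycemia after the pre-procedure ECG, and palpitations are listed among its symptoms (2.1.1). Placebo subjects may stay hypoglycemic longer. Neither the size nor the sign of the net heart-rate difference can be derived from the protocol.
- **That a planned QTc comparison is invalid.** The protocol has no QTc endpoint, threshold, outlier count or test.
- **That the ECG times sit at peak heart-rate effect.** They coincide with median peak plasma concentration. Timing of the heart-rate effect is not reported.

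The size of the artefact also depends on an exponent that the protocol does not give. It vanishes at 0.50 and reverses above that.

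**Conclusion.** The point holds as a minor one. Naming Bazett as the sole rate correction is a weak choice in a trial whose own background section raises a possible chronotropic effect. If QT follows RR with an exponent below 0.5, any between-arm difference in heart-rate change is carried into the QTcB summaries. For an assumed net difference of 10 bpm the carry-over is about 15 ms at exponent 0.25, 10 ms at 1/3, 6 ms at 0.40 and 0 at 0.50, with the sign set by whichever arm has the larger rise. The preference for QTcF assumes an exponent nearer 1/3 than 1/2, which is a reason to keep both. What is affected is the descriptive ECG summaries and, possibly, significance and adverse-event calls. Efficacy conclusions are untouched.

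**What to change.** In section 7.2.5, add QTcF, calculated from the recorded QT and heart rate as QT/RR^(1/3) with RR = 60/HR. In section 9.7.4, name QTcF as the main corrected interval in the descriptive ECG summaries by arm, and keep QTcB as supportive or in listings. Summarize ECG heart rate by arm alongside, so that a reader can see whether a QTc difference tracks a rate difference.

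The cost is one derived variable, with no new ECGs and no new data entry. If the value is derived only at analysis, it corrects the summaries but not ratings already made. For it to inform those, it has to be available when the ECG is rated, which is why the change belongs in 7.2.5 as well as 9.7.4.
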